8.3.4. Treatment of adverse events

Any medication which may explain/cause/be used to treat an SAE/pIMD should be recorded in the Expedited Adverse Event Report of the participant's eCRF screen (refer to Section 10.3.10.1).

8.3.5. Participant card

The investigator (or designee) must provide the participant with a "participant card" containing information about the clinical study. The participant must be instructed to keep the participant card in his/her/their possession at all times throughout the study. In an emergency, this card serves to inform the responsible attending physician/caregiver/family member that the participant is in a clinical study and that relevant information may be obtained by contacting the investigator.

^{**}Timeframe allowed once the investigator determines that the event meets the protocol definition of an pIMD.

[#]The investigator will be required to confirm review of the SAE/pIMD causality by ticking the 'reviewed' box in the electronic Expedited Adverse Events Report within 72 hours of submission of the SAE/pIMD.

8.4. Treatment of overdose

This section is not applicable.

8.5. Pharmacokinetics

Pharmacokinetic parameters are not evaluated in this study.

8.6. Pharmacodynamics

Pharmacodynamic parameters are not evaluated in this study.

8.7. Genetics

Genetics are not evaluated in the current study. For participants who consent to participate in genetic research in future studies, the obtained blood samples may be used at a later stage in future studies for research such as B cell receptor repertoire analysis (B cell receptor sequencing).

8.8. Biomarkers

Biomarkers for pharmacogenetics are not evaluated in this study.

8.9. Health outcomes

Economic outcome measures such as health care resource utilization data associated with healthcare encounters are not evaluated in this study.

9. STATISTICAL CONSIDERATIONS

9.1. Statistical hypotheses

Not applicable as this study is descriptive.

9.2. Sample size determination (Amended: 01 April 2022)

This study is planned to enroll ~1650 participants randomized according to 3:1:1 ratio to 1 of the 3 study groups: RSV_annual, RSV_flexible revaccination, and RSV_1dose respectively.

The proposed sample size is based on the following considerations:

• Ensure a sufficient number of participants to evaluate with adequate precision the immunogenicity after a single dose regimen up to 12 months post-vaccination (based on the 3 pooled RSV_annual, RSV_flexible revaccination and RSV_ldose groups) but also the immunogenicity after revaccination (based on RSV_annual and RSV_flexible revaccination groups).

- Ensure adequate description of the antibody kinetics after a single dose keeping the flexibility to give a revaccination to a part of the participants.
- Ensure an adequate sample size for evaluation of reactogenicity and safety profile following revaccination.

Approximately 345 participants will be enrolled in the humoral subset in the RSV_annual group and approximately 330 participants per group in the RSV_flexible revaccination and RSV_1dose groups. Approximately 345, 115 and 115 participants will be enrolled in the CMI subset in the RSV_annual, RSV_flexible revaccination, and RSV_1dose groups, respectively. A total of 990 and 330 participants will be enrolled in the RSV_annual and RSV_flexible revaccination groups, respectively, for evaluation of reactogenicity and safety profile following revaccination. A 20% rate of non-evaluable participants every year will be considered.

Withdrawals will not be replaced.

9.2.1. Evaluation of humoral immune response up to Month 12 (primary objective and first secondary objective)

At Month 12, the effect of a 1-dose primary schedule will be evaluated in terms of RSV-A/B neutralizing antibody titers and RSVPreF3-specific IgG concentrations. Approximately 804 participants in the (RSV_annual, RSV_flexible revaccination, and RSV_1dose) pooled group receiving a single dose of RSVPreF3 OA investigational vaccine will be evaluable for the humoral immune response at Month 12.

Table 17 shows the precision that can be obtained based on different values of standard deviations in terms of RSV-A/B neutralizing antibody titers, and RSVPreF3-specific IgG antibody concentrations.

Table 17 Precision and 95% confidence interval on the geometric mean antibody titers and concentrations at Month 12 based on different values of standard deviations for 804 evaluable participants in the (RSV_annual, RSV_flexible revaccination and RSV_1dose) pooled groups

Number of enrolled participants in the humoral subset (3 groups pooled*)	Number of evaluable participants in the humoral subset up to Month 12 (3 groups pooled*)	Standard deviation in log10	Width ½ 95% CI in log10	Ratio upper limit 95% CI/GM	Ratio upper limit/ lower limit 95% CI
1005	804	0.30	0.021	1.05	1.10
1005	804	0.35	0.024	1.06	1.12
1005	804	0.40	0.028	1.07	1.14
1005	804	0.45	0.031	1.07	1.15
1005	804	0.50	0.035	1.08	1.17

^{*}At the time of the analysis at Month 12 (RSV_annual, RSV_flexible revaccination and RSV_1dose groups) will be pooled.

Precision estimated using PASS 12.0.10: Confidence interval of a mean, alpha = 5%.

CI = Confidence Interval, LL = Lower Limit, UL = Upper Limit

GM = Geometric Mean

9.2.2. Evaluation of the cellular immune response up to Month 12 (secondary objective)

At Month 12, the effect of a 1-dose primary schedule dose will be evaluated in terms of RSVPreF3-specific CD4+ T cells frequency. Approximately, 460 participants in the pooled groups (RSV_annual, RSV_flexible revaccination, and RSV_1dose groups) receiving a single dose of RSVPreF3 OA investigational vaccine will be evaluable for the CMI response at study Month 12.

Table 18 shows the precision that can be obtained based on different values of standard deviations in terms of the frequency of RSVPreF3-specific CD4+ T cells.

Table 18 Precision and 95% confidence interval on the geometric mean of the frequency of RSVPreF3-Specific CD4+ T cells at Month 12 based on different values of standard deviations for 460 evaluable participants in the (RSV_annual, RSV_flexible revaccination and RSV_1dose) pooled groups

Number of enrolled participants in the CMI subset (3 groups pooled*)	Number of evaluable participants in the CMI subset up to Month 12 (pooled 3 groups pooled*)	Standard deviation in log10	Width ½ 95% CI in log10	Ratio upper limit 95% CI/GM	Ratio upper limit/ lower limit 95% CI
575	460	0.30	0.027	1.06	1.13
575	460	0.35	0.032	1.08	1.16
575	460	0.40	0.037	1.09	1.19
575	460	0.45	0.041	1.10	1.21
575	460	0.50	0.046	1.11	1.24

^{*}At the time of the analysis at Month 12 (RSV_annual, RSV_flexible revaccination and RSV_1dose groups) will be pooled.

Precision estimated using PASS 12.0.10: Confidence interval of a mean, alpha = 5%.

CI = Confidence Interval, LL=Lower Limit, UL=Upper Limit

GM = Geometric Mean

9.2.3. Evaluation of humoral and cellular immune response at Month 13 (secondary objective)

At Month 13 (one month post-revaccination at Month 12), the effect of a revaccination dose will be evaluated. As such \sim 276 participants in the RSV_annual group receiving a revaccination dose of RSVPreF3 OA investigational vaccine will be evaluable for the humoral and cellular immune response at study Month 13.

Table 19 shows the precision that can be obtained based on different values of standard deviations in terms of RSV-A/B neutralizing antibody titers, RSVPreF3-specific IgG antibody concentrations and the frequency of RSVPreF3-specific CD4+ T cells.

Table 19 Precision and 95% confidence interval on the geometric mean antibody titers/concentrations and of the frequency of RSVPreF3-Specific CD4+ T cells at Month 13 based on different values of standard deviations for 276 evaluable participants in the RSV_annual group

Number of enrolled participants in the humoral and CMI subsets in the RSV_annual	Number of evaluable participants in the humoral and CMI subsets at Month 13	Standard deviation in log10	Width ½ 95% CI in log10	Ratio upper limit 95% CI/ GM	Ratio upper limit/ lower limit 95% CI
345	276	0.30	0.036	1.09	1.18
345	276	0.35	0.041	1.10	1.21
345	276	0.40	0.047	1.11	1.24
345	276	0.45	0.053	1.13	1.28
345	276	0.50	0.059	1.15	1.31

Precision estimated using PASS 12.0.10: Confidence interval of a mean, alpha = 5%.

CI = Confidence Interval, LL = Lower Limit, UL = Upper Limit

GM = Geometric Mean

9.2.4. Evaluation of humoral and cellular immune response at Month 25 in the RSV_annual and RSV_flexible revaccination groups (secondary objective) (Amended: 01 April 2022)

At Month 25 (one month post-revaccination at Month 24), the effect of revaccination dose will be evaluated.

As such ~220 participants in the RSV_annual group receiving a revaccination dose of RSVPreF3 OA investigational vaccine will be evaluable for the humoral and cellular immune response at study Month 25.

Table 20 shows the precision that can be obtained based on different values of standard deviations in terms of RSV-A/B neutralizing antibody titers, RSVPreF3-specific IgG antibody concentrations and the frequency of RSVPreF3-specific CD4+ T cells.

Approximately 211 participants in the RSV_flexible revaccination group receiving a revaccination dose of RSVPreF3 OA investigational vaccine will be evaluable for the humoral immune response at study Month 25. Table 21 shows the precision that can be obtained based on different values of standard deviations in terms of RSV-A/B neutralizing antibody titers, RSVPreF3-specific IgG antibody concentrations.

Approximately 74 participants in the RSV_flexible revaccination group receiving a revaccination dose of RSVPreF3 OA investigational vaccine will be evaluable for the cellular immune response at study Month 25. Table 22 shows the precision that can be obtained based on different values of standard deviations in terms of the frequency of RSVPreF3-specific CD4+ T cells.

212496 (RSV OA=ADJ-004) Protocol Amendment 1 Final

Table 20 Precision and 95% confidence interval on the geometric mean antibody titers/concentrations and of the frequency of RSVPreF3-specific CD4+ T cells at Month 25 based on different values of standard deviations for 220 evaluable participants in the RSV_annual group

Number of enrolled participants in the humoral and CMI subsets in the RSV_annual	Number of evaluable participants in the humoral and CMI subsets at Month 25	Standard deviation in log10	Width ½ 95% CI in log10	Ratio upper limit 95% CI/GM	Ratio upper limit/ lower limit 95% CI
276	220	0.30	0.040	1.10	1.20
276	220	0.35	0.047	1.11	1.24
276	220	0.40	0.053	1.13	1.28
276	220	0.45	0.060	1.15	1.32
276	220	0.50	0.066	1.16	1.36

Precision estimated using PASS 12.0.10: Confidence interval of a mean, alpha = 5%.

CI = Confidence Interval, LL = Lower Limit, UL = Upper Limit

GM = Geometric Mean

Table 21 Precision and 95% confidence interval on the geometric mean antibody titers/concentrations at Month 25 based on different values of standard deviations for 211 evaluable participants in the RSV_flexible revaccination group

Number of enrolled participants in the humoral subset in the RSV_flexible	humoral subset at	Number of evaluable participants in the humoral subset at		Width ½ 95% CI in log10	Ratio UL 95% CI / GM	Ratio UL / LL 95% CI
revaccination	Month 13	Month 25				
330	264	211	0.30	0.041	1.10	1.21
330	264	211	0.35	0.047	1.11	1.24
330	264	211	0.40	0.054	1.13	1.28
330	264	211	0.45	0.061	1.15	1.32
330	264	211	0.50	0.068	1.17	1.37

Precision estimated using PASS 2019: Confidence interval for one mean, alpha = 5%. CI = Confidence Interval, LL = Lower Limit, UL = Upper Limit; GM = Geometric Mean

Table 22 Precision and 95% confidence interval of the frequency of RSVPreF3-specific CD4+ T cells at Month 25 based on different values of standard deviations for 74 evaluable participants in the RSV_flexible revaccination group

Number of enrolled participants in the CMI subset in the RSV_flexible revaccination group	Number of evaluable participants in the CMI subset at Month 13	Number of evaluable participants in the CMI subset at Month 25	Standard deviation in log10	Width ½ 95% CI in log10	Ratio UL 95% CI / GM	Ratio UL / LL 95% CI
115	92	74	0.30	0.070	1.17	1.38
115	92	74	0.35	0.081	1.21	1.45
115	92	74	0.40	0.093	1.24	1.53
115	92	74	0.45	0.105	1.27	1.62
115	92	74	0.50	0.116	1.31	1.71

Precision estimated using PASS 2019: Confidence interval of a mean, alpha = 5%. CI = Confidence Interval, LL = Lower Limit, UL = Upper Limit; GM = Geometric Mean

9.2.5. Evaluation of reactogenicity and safety profile following revaccination in the RSV_annual and RSV_flexible revaccination groups (Amended: 01 April 2022)

As indicated in Table 23, the proposed sample sizes of 990 participants in the RSV_annual group receiving revaccination on an annual basis and 330 participants in the RSV_flexible revaccination group receiving revaccination at Year 2 (Month 24), give 99.3% and 80.9% probabilities, respectively, of observing at least one AE if a true incidence rate equals 0.5%. This probability increases to 100% for true incidence rates $\geq 0.8\%$ for the RSV_annual group. Although lower, the probability remains above 62% to detect at least one AE that would occur at a frequency of 0.1% (1/1000) and 0.3% (3/1000) in the RSV annual and RSV flexible revaccination groups, respectively.

Table 23 Probability (%) to observe at least one AE depending on the AE true incidence rate with 990 and 330 participants in the RSV_annual and RSV_flexible revaccination groups, respectively

Incidence rate	Probability to observe at least one AE in the RSV_annual	Probability to observe at least one AE in the RSV_flexible revaccination
0.01%	9.4%	3.2%
0.05%	39.1%	15.2%
0.10%	62.9%	28.1%
0.15%	77.4%	39.1%
0.20%	86.2%	48.3%
0.25%	91.6%	56.2%
0.30%	94.9%	62.9%
0.35%	96.9%	68.6%
0.40%	98.1%	73.4%
0.50%	99.3%	80.9%
0.60%	99.7%	86.3%
0.70%	99.9%	90.2%
0.80%	100.0%	92.9%
0.90%	100.0%	94.9%
1.00%	100.0%	96.4%

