9.3. Populations for analyses (Amended: 01 April 2022)

Table 24 Populations for analyses (Amended: 01 April 2022)

Analysis set	Description		
Enrolled set	Participants who agreed to participate in a clinical study after completion of the informed consent process .		
Exposed set (ES)	All participants who received at least 1 dose of the study intervention. The allocation in a group is done in function of the administered intervention.		
Per-Protocol set (PPS)	All participants who received at least 1 dose of the study intervention to which they are randomized and have post-vaccination immunogenicity data, minus participants with protocol deviations that lead to exclusion.		

The primary analysis for immunogenicity will be performed on the PPS. If in any study group *and for at least one visit*, the percentage of vaccinated participants with serological results excluded from the PPS for immunogenicity is at least 5%, a second analysis will be performed on the ES. The immunogenicity analysis will be performed, overall, by sex,

212496 (RSV OA=ADJ-004) Protocol Amendment 1 Final

by age category (age at Dose 1: \geq 65 YOA, \geq 70 YOA, \geq 80 YOA, 60-69 YOA and 70-79 YOA), and by region.

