a clinical study following completion of the informed consent process. Potential participants who are screened for the purpose of determining eligibility for the study, but do not participate in the study, are not considered enrolled, unless otherwise specified by the protocol. Refer to the Section 9.3 for the definition of 'enrolled' applicable to the

study.

Essential documents: Documents which individually and collectively permit

evaluation of the conduct of a study and the quality of the

data produced.

eTrack: GSK's tracking tool for clinical trials.

Evaluable: Meeting all eligibility criteria, complying with the

procedures defined in the protocol, and, therefore, included in the per-protocol analysis (see Section 9.3 for details on

criteria for evaluability).

Former smoker: A person who stopped smoking for at least 6 months at the

time of study start.

Immunological

correlate of protection: certain level of protection from the targeted endpoint.

Intervention: Term used throughout the clinical study to denote a set of

investigational product(s) or marketed product(s) or placebo intended to be administered to a participant.

A correlate of risk that has been validated to predict a

Intervention number: A number identifying an intervention to a participant,

according to intervention allocation.

Invasive medical

device:

A device which, in whole or in part, penetrates inside the body, either through a body orifice or through the surface

of the body.

Investigational vaccine: A pharmaceutical form of an active ingredient being tested

in a clinical trial, including a product with a marketing authorization when used in a way different from the approved form, or when used for an unapproved indication,

or when used to gain further information about an

approved use.

Synonym: Investigational Medicinal Product

212496 (RSV OA=ADJ-004) Protocol Amendment 1 Final

Investigator:

A person responsible for the conduct of the clinical trial at a trial site. If a trial is conducted by a team of individuals at a trial site, the investigator is the responsible leader of the team and may be called the principal investigator.

The investigator can delegate trial-related duties and functions conducted at the trial site to qualified individual or party to perform those trial-related duties and functions.

Long-term care facility (LTCF):

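### Protocol 9.2.5 and Table 23 give best-case per-dose chances of seeing an AE after revaccination, because they use the numbers enrolled at Day 1 with no allowance for missed doses

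*Protocol*

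**What the plan says.** Protocol 9.2 gives the source of the safety numbers: "A total of 990 and 330 participants will be enrolled in the RSV_annual and RSV_flexible revaccination groups, respectively", for evaluating reactogenicity and safety after revaccination. The next two statements are "A 20% rate of non-evaluable participants every year will be considered" and "Withdrawals will not be replaced".

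Section 9.2.5 then treats the same counts as people who have been revaccinated: "the proposed sample sizes of 990 participants in the RSV_annual group receiving revaccination on an annual basis and 330 participants" in RSV_flexible. It reports 99.3% and 80.9% probabilities of at least one AE at a true incidence of 0.5%. It adds that "the probability remains above 62% to detect at least one AE that would occur at a frequency of 0.1" per cent in RSV_annual, or 0.3% in RSV_flexible. Table 23 tabulates 15 incidence rates for each group on these two counts.

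Tables 17 to 22, for immunogenicity, do use reduced numbers. For RSV_flexible, 330 becomes 264 and then 211, the last described as participants "receiving a revaccination dose of RSVPreF3 OA investigational vaccine will be evaluable for the humoral immune response at study Month 25".

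Safety is analysed on the Exposed Set, defined as "All participants who received at least 1 dose of the study intervention", and tabulated after each dose (Protocol 9.3 and 9.4.4.3).

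**The concern.** A participant who does not receive the Month 12 or Month 24 dose cannot contribute an event following it. The Exposed Set does not solve this: someone vaccinated only at Day 1 stays in the set but adds nothing to the post-revaccination tabulation.

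Missed doses are foreseen throughout the plan. Protocol 7.1 defines discontinuation of intervention as not receiving all planned doses, and 7.1.2 lists contraindications to later doses. SAP Amendment 3, Section 5, has a provision for when more than 5% receive differing numbers of doses. Its Section 5.4.6 has another for when more than 10% miss revaccination or lack safety data after it.

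Adequate size for post-revaccination safety is one of the three sample-size considerations listed in 9.2, and Table 23 is its only numerical support. At stake is how rare an event the plan says it can pick up after each revaccination dose. Nothing in 9.2.5 tells the reader that the figures assume full uptake.

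**Working it through.** **Inputs.** n = 990 and 330 (Protocol 9.2, 9.2.5, Table 23); true rates of 0.1%, 0.3% and 0.5% (9.2.5). The 5% and 10% missed-dose levels are borrowed from SAP Sections 5 and 5.4.6, where they are triggers for extra analyses and not expected rates. The 20% per year is from 9.2.

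**Formula.** P(at least one AE) = 1 − (1 − p)^n.

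**Reproducing the plan.**
- RSV_annual, 0.5%: 1 − 0.995^990 = 99.30% (stated 99.3%).
- RSV_flexible, 0.5%: 1 − 0.995^330 = 80.87% (stated 80.9%).
- RSV_annual, 0.1%: 1 − 0.999^990 = 62.86% (stated 62.9%).
- RSV_flexible, 0.3%: 1 − 0.997^330 = 62.90% (stated 62.9%).

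All 30 cells of Table 23 reproduce to within rounding, so no deduction was made.

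**When the above-62% statement fails, per dose.**
- RSV_flexible, 0.3%: 330 − 8 = 322, and 1 − 0.997^322 = 61.99%. The loss is 8/330 = 2.4%.
- RSV_annual, 0.1%: 990 − 23 = 967, and 1 − 0.999^967 = 61.996%. The loss is 23/990 = 2.3%.

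The two groups fall together because the expected event count is the same: 330 × 0.003 = 990 × 0.001 = 0.99.

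**Scenarios, per dose.**

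| Missed dose | RSV_flexible n | at 0.3% | at 0.5% | RSV_annual n | at 0.1% | at 0.5% |
|---|---|---|---|---|---|---|
| None (Table 23) | 330 | 62.9% | 80.9% | 990 | 62.9% | 99.3% |
| 5% | 313 | 61.0% | 79.2% | 940 | 61.0% | 99.1% |
| 10% | 297 | 59.0% | 77.4% | 891 | 59.0% | 98.9% |

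**Pessimistic illustration only, carrying over 20% per year.** 330 × 0.64 gives 211; 990 × 0.80 = 792 at Month 12; 990 × 0.64 gives 634 at Month 24. RSV_flexible is then 47.0% at 0.3% and 65.3% at 0.5%. RSV_annual at 0.1% is 54.7% (Month 12) and 47.0% (Month 24); at 0.5% it is 98.1% and 95.8%.

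**RSV_annual over both revaccination doses, at 0.1%, assuming independence between doses.** No loss: 990 + 990 = 1980, giving 86.2%. 10% per year: 891 + 802 = 1693, giving 81.6%. 20% per year: 792 + 634 = 1426, giving 76.0%.

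**Zero events in RSV_flexible.** The upper limit of the two-sided 95% Clopper-Pearson interval (SAP 10.1.5.1) is 1 − 0.025^(1/n): 1.11% for n = 330 and 1.23% for n = 297.

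**The case against.** The strongest reply is that nothing is miscalculated and nothing is hidden. The title of Table 23 names 990 and 330, and the study is descriptive (Protocol 9.1), so no test or decision depends on the table. Doses given are tabulated by group and visit, AE percentages carry exact intervals after each dose, and the SAP has provisions for missed doses. Actual exposure will therefore be visible in the results. All of that stands, and it limits the importance of the point. It does not make the enrolled participants revaccinated ones, which is how 9.2.5 describes them.

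A reader might infer that the plan's own 20% yearly rate should have reduced Table 23 to 211, 792 and 634, making the printed figures badly overstated. The documents do not support that. The glossary defines evaluable participants as those complying with the "procedures defined in the protocol, and, therefore, included in the per-protocol analysis", whereas safety needs only vaccination. A participant can be outside the per-protocol set and still be revaccinated and followed for safety. Those counts are at most a labelled pessimistic scenario.

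A reader might also infer that only RSV_flexible is affected. At 0.5% that is fair, because RSV_annual has ample margin. For the above-62% sentence it is not: per dose, both groups fall equally. RSV_annual escapes only if its two doses are counted together. Section 9.2.5 does not state such a basis, and Table 23 does not use the corresponding 1980.

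Finally, the requirement for a completed diary (Protocol 9.4.1.3) reduces n further for solicited events only. For unsolicited AEs, SAEs and pIMDs all vaccinated participants count.

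**Conclusion.** The point holds as one about the denominator. Table 23 is arithmetically correct for 990 and 330, but as a statement about AEs following revaccination it is the best case per dose, in both groups, and is not labelled as such. The above-62% sentence does not survive a loss of about 2.4%, which is below both levels at which the SAP contemplates extra analyses.

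The supportable size is modest: about 2 to 4 percentage points with 5% to 10% of doses missed, and under half a point for RSV_annual at 0.5%. This rests on assumed missed-dose levels, since the documents give no expected number revaccinated at Month 12 or Month 24. It does not show that the safety database is too small, and it touches no hypothesis, decision rule or planned analysis. The stated detection probabilities should nonetheless be corrected.

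**What to change.** - Label the current Table 23 as assuming that every enrolled participant is revaccinated.
- Add per-dose columns for the number the sponsor expects to receive each revaccination dose (RSV_annual at Month 12, RSV_annual at Month 24, RSV_flexible at Month 24). State the missed-dose rate assumed or, if none can be justified, show a range such as 5% and 10%.
- Replace the above-62% sentence in 9.2.5 with the recomputed figures for both groups.
- If the 20%-per-year counts are shown, mark them as a pessimistic scenario derived from a per-protocol rate.
- If RSV_annual is also to be described over both doses, give that n and its basis separately.

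The cost is one restated table and a few sentences, plus a sponsor assumption on uptake that the documents do not yet contain. The stated figures become slightly less favourable. No participants are added, and design and analysis stay as they are.
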